## **Endpoints**

Successful placement of peripheral radial arterial catheter as evidenced by transduction of arterial waveform on bedside monitor.

## **Primary Outcome**

First-stick success rate of ultrasound-guided peripheral arterial catheter placement.

## **Secondary Outcomes**

- Number of attempts to achieve successful arterial catheter cannulation; “attempt” will be defined as a single insertion of the needle into the skin.
- Amount of time required for successful arterial catheter cannulation.
- Number of failed attempts leading to unsuccessful arterial catheter cannulation
- Subjective response from anesthesia provider regarding their experience utilizing a single-plane versus a dual-plane ultrasound probe.
  - Please explain your experience using this ultrasound probe.
  - If you used the dual-view probe, how do you feel that this dual-view probe impacted your procedure as compared to a single-view ultrasound probe?

- Do you feel that the dual-view ultrasound probe provides a procedural benefit over the single-view ultrasound probe; please explain.

## **V. Data, Safety, and Monitoring Plan**

### **Data Collection**

The data collected for this study will be:

- Number of attempts to achieve successful arterial catheter cannulation; “attempt” will be defined as a single insertion of the needle into the skin.
- Amount of time required for successful arterial catheter cannulation.
- Number of failed attempts leading to unsuccessful arterial catheter cannulation
- Subjective response from anesthesia provider regarding their experience utilizing a single-plane versus a dual-plane ultrasound probe.
- Level of training of anesthesia provider: Trainee, CRNA, Attending physician

This data will be recorded on a paper form in the operating room at the time of surgery; the paper form will then be transcribed into RedCap by a member of the research team. No patient-specific or provider-specific data will be collected.

### **Feasibility and Time Frame**

Given the high incidence of peripheral arterial catheter placement during elective cases in the main operating room at both Saint Mary’s Campus and the Rochester Methodist Campus (approximately 75-100 per day); we will plan to collect this data over the course of 2 months pending sufficient enrollment.

### **Subject Safety**

Enrolled patients will be exposed to minimal additional risk. The additional risk may include additional peripheral arterial catheter placement attempts which may lead to hematoma formation, bleeding, artery injury, and necessitation to identify alternative anatomic sites for successful arterial catheter placement.

There will be no additional risk posed to the anesthesia providers.

Given the fact that this is considered a low-risk intervention, we will apply for a waiver of documentation of informed consent from the patient and anesthesia provider.

### **Monitoring**

No additional patient monitoring will be required for this study.

### **Data Integrity**

All clinical data will be entered and compiled in a secure database maintained by the principal investigator, co-investigators, and study coordinator. This database will be located in the Mayo Clinic intranet, behind the Mayo Clinic firewall and restricted only to authorized research group members by password. No laptops, USB and/or websites will be used.

### **Data Confidentiality**

All data recorded on paper forms at the time of surgery will be transcribed by a member of the research team into a RedCap database. Immediately following transcription, the paper data copy will be destroyed. Access to the RedCap database will be limited to the research team and study coordinator.

### **Strengths**

This study is simple, short, and straightforward and should be completed within a year—more likely within six months. The study will be used to evaluate the potential beneficial impact of a dual-plane ultrasound probe and its impact on efficiency and success of vascular catheter placement procedures. Pending positive results from this study, consideration of incorporating dual-plane imaging training into central line placement courses and peripheral catheter placement practices (PIVC / PICC / Midline). This will also serve as the first identifiable randomized trial in the literature comparing simultaneous dual-plane ultrasound imaging versus single-plane ultrasound imaging in vascular access procedures.

Dual-plane Ultrasound Imaging During Vascular Access Procedures

NCT05093699

September 1, 2023

Statistical Analysis Plan

Quantitative, patient-outcomes:

Continuous outcome summarized using mean and category outcome summarized via frequency. Log transformation analysis used to satisfied distribution all assumptions. Assessed via on adjusted linear regression. Exploratory analysis. Statistical significance determined by two-tailed p-values of 0.05 or less. Data management and statistical analyses were performed in SAS 9.4

Qualitative, provider-response questions:

Theme based analysis utilizing verbatim responses. Assignment of code numbers to the themes and application two individual responses. Frequency of theme in total and subgroup analysis to be reported.

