## **IV. Research Design and Methods**

### **Study Design**

This investigation will employ a prospective, non-blinded randomized-control study.

Study Subjects – 50 patients who meet enrollment criteria.

Control Subjects – 50 patients who meet enrollment criteria.

Provider subjects – Up to 50 anesthesia providers (trainee, CRNA, anesthesia staff physician)

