## **Methods**

Anesthesia providers assigned to an upcoming rotation in the main operating rooms will receive a recruitment message via e-mail regarding participation in this study. If they consent to participate, they will be asked to view an online educational video sent to them via email (see below) and will be given an opportunity to practice use of the dual-view probe prior to use on a patient. Some providers may have utilized the dual-view technology previously.

Instructional Video for Providers: <https://www.youtube.com/watch?v=rBS3Galrqqc>

Enrolled patients will be randomized to two groups:

Protocol version v5 11022021

- Control: Arterial line placement via “standard” mechanism; utilization of a single-plane ultrasound probe
- Intervention: Arterial line placement utilizing dual-plane, Butterfly iQ+ ultrasound probe.

A Butterfly iQ+ with attached large iPAD or alternate tablet device will be utilized for this study to allow for a larger screen visualization as compared to a portable phone device.

The anesthesia provider (attending physician, CRNA, or trainee) staffed in the patient’s operating room will place the arterial line using standard practice besides randomization to the type of ultrasound probe. It will be recorded if the provider has previously utilized the dual-view probe.

The anesthesia residency program is already providing their trainees with an individual Butterfly iQ+ ultrasound probe system; therefore, these already purchased and implemented devices will be utilized in this study.

The research coordinator will utilize a stopwatch to record the amount of time required for successful placement of a peripheral arterial catheter; time recording will begin with the initial skin puncture and cease with observation of an appropriate arterial waveform on the in-room monitor.

If a patient is enrolled in the “Intervention” group and the anesthesia provider requires more than 3 attempts to achieve successful arterial catheter cannulation; the provider will discontinue use of the dual-plane probe and attempt placement with a technique of their choosing.

A picture of the ultrasound image at the completion of the procedure, successful or unsuccessful, will be obtained; no patient-specific information will be recorded.

All data will be collected, organized, and analyzed with the aid of a dedicated biostatistician from the Health Science Research office. Estimate for their work are included in the attached budget.

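### The SAP states no clear comparison for the binary primary outcome, and operator training level, though collected, has no stated role in randomisation or in the quantitative analysis

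*SAP*

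**What the plan says.** The protocol's Primary Outcome section names "First-stick success rate of ultrasound-guided peripheral arterial catheter placement", which is success or failure for each patient. Study Design plans 50 patients per arm in a "prospective, non-blinded randomized-control study".

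Under Methods, "Enrolled patients will be randomized to two groups", with no stratification or blocking factor given. The same section says that the provider staffed in the patient's operating room, who may be an attending physician, CRNA or trainee, "will place the arterial line using standard practice besides randomization to the type of ultrasound probe". Data Collection lists "Level of training of anesthesia provider: Trainee, CRNA, Attending physician".

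The quantitative part of the SAP is a few sentences. Continuous outcomes get a mean and "category outcome summarized via frequency". A log transformation is mentioned without saying for which outcome. The model sentence is "Assessed via on adjusted linear regression". The work is labelled "Exploratory analysis", and a two-tailed 0.05 threshold is set. The SAP does not name the primary outcome, a covariate, an effect measure or a confidence interval.

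**The concern.** There are two linked gaps.

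- **No clear comparison for the primary outcome.** If the regression sentence is meant for continuous outcomes only, first-stick success has a frequency table and a significance threshold but no test. If the sentence covers all outcomes, the reader cannot tell whether the model is adjusted. Read as "an adjusted" model, it lacks its covariates. Read as "unadjusted", it leaves out a variable that is already collected and plausibly prognostic.
- **No stated role for training level.** Operators range from trainee to attending physician. With 50 per arm and no stated stratification, the operator mix can differ between arms by chance, and neither the model nor a planned table would account for it or show it.

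At stake are some precision, and the reader's ability to check that the arms had similar operators.

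**Working it through.** The plan has no figure to reproduce: 50 per arm is given without a control rate, target difference or power. Success rates by training level and trainee shares below are assumptions.

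**1. Is a linear model on 0/1 data a problem in itself?** Exact enumeration at 50 per arm, two-sided 0.05, with common success rates of 18%, 50%, 70%, 79% and 90%, gives type I error of 4.8% to 5.7% for an unadjusted linear model and 5.0% to 5.7% for chi-square. Power differs by about 1 point at most (70% vs 90%: 72.4% and 73.5%; 60% vs 80%: 59.5% for both). An untransformed linear model is therefore close to nominal and estimates a risk difference.

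**2. Variance explained by training level.** With trainee share s, success rates differing by *gap*, and overall rate p, R² = s(1−s)·gap² / [p(1−p)]. The equivalent sample size per 100 patients is 100/(1−R²). For s = 0.5:

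| Trainee / other success | p | R² | Equivalent N |
|---|---|---|---|
| 55% / 70% | 0.625 | 0.25 × 0.0225 / 0.2344 = 0.024 | 102.5 |
| 50% / 70% | 0.600 | 0.25 × 0.0400 / 0.2400 = 0.042 | 104.3 |
| 50% / 75% | 0.625 | 0.25 × 0.0625 / 0.2344 = 0.067 | 107.1 |

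Trainee shares of 30% or 70% give 102.0 to 106.4. Adjustment is worth about 2 to 7 patients per 100.

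**3. Power.** This was simulated with 50 per arm, s = 0.5 and a true gain of 20 points, comparing the unadjusted test with a Mantel-Haenszel test stratified by trainee status (size 0.050):

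- 15-point gap: 62.2% vs 62.9%, a gain of about 0.6 points (0.7 from the rounded figures)
- 20-point gap: 59.6% vs 61.3%, a gain of 1.7 points
- 25-point gap: 62.1% vs 65.2%, a gain of 3.1 points

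**4. Chance imbalance.** The SD of the between-arm difference in trainee share is √[2s(1−s)/50]. This is 0.100 for s = 0.5 and 0.092 for s = 0.3 or 0.7. The exact probability of a difference of 20 points or more is 0.057 and 0.038 respectively, so about 4% to 6% of trials. With a 20-point skill gap, such a difference moves the unadjusted estimate by 0.20 × 0.20 = 4 points. For scale, the standard error of the arm difference at p = 0.6 is √(2 × 0.24/50) = 9.8 points, so the shift is about 0.4 of a standard error. With rates of 50% and 70%, type I error conditional on 20 vs 30 trainees is 0.067, against 0.047 for 25 vs 25.

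**5. Cost if training level does not predict success.** At 60% for both groups, the simulated variance of the unadjusted risk difference over that of the standardised one is 0.99. Adjusting then costs about 1 patient per 100.

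**The case against.** The strongest case against is that an unadjusted analysis of a randomised comparison is valid. Omitting a covariate that explains 2% to 7% of variance is a choice and not an error. The SAP calls the work exploratory, and its past tense suggests the analysis has been run. Every magnitude above is assumed, and the calculations treat patients as independent although up to 50 providers serve 100 patients. All of this stands, and it is why the point is minor. It does not supply the missing method: a plan that sets a significance threshold should say how its primary outcome is compared.

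A reader might infer more than the documents support:

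- **That linear regression is invalid here.** Step 1 shows otherwise.
- **That the SAP log-transforms a 0/1 outcome.** Log of zero is undefined, but the SAP does not say the transformation applies to first-stick success. It may be meant only for a continuous outcome such as procedure time.
- **That operators were chosen after the open allocation was seen.** Methods says the staffed provider places the line, with only the probe randomised. It does not say when the arm is revealed, so selection is not shown.
- **That the power gain is larger.** A likelihood-ratio test in a logistic model shows gains of 1.8, 3.0 and 4.4 points in the three cases, but its size is 0.052 to 0.053, so part of the gain is test size.
- **That training level is absent from the whole SAP analysis.** The provider-response part mentions subgroups without defining them, and training level might be one. The gap is in the quantitative part.

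**Conclusion.** The point holds as a minor one. Under either reading of the regression sentence, the primary comparison is not clearly specified, and a collected, plausibly prognostic variable has no stated role in randomisation or in the quantitative analysis. Provided staffing fixes the operator, expected bias is zero and the unadjusted test keeps its overall type I error. The statistical loss is small: about 2 to 7 patients per 100 and about 0.6 to 3 points of power, with a shift of about 4 points in the 4% to 6% of trials where trainee share differs by 20 points or more (exactly 4 points at a 20-point difference). These figures rest on assumed skill gaps of 15 to 25 points (20 for the shift). The power gains assume half the operators are trainees, and the imbalance range covers trainee shares of 30% to 70%. If training level does not predict success, there is nothing to gain.

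**What to change.** In the SAP:

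1. Compare first-stick success by a risk difference adjusted for operator training level, with a confidence interval. A Mantel-Haenszel stratified analysis would do, or logistic regression with a standardised risk difference.
2. Analyse log procedure time by linear regression adjusted for training level.
3. Report the unadjusted result beside each adjusted one.
4. Tabulate training level by arm.
5. Label the covariate choice post hoc if it was made after data were seen. The SAP is dated September 2023 and describes analyses as already performed.

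The cost is SAP wording and one table from a variable already collected, plus about 1 patient per 100 of precision if training level turns out not to predict success.
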